4.5 Description of rules for permanent or temporary discontinuation

4.5.1Discontinuation of participation of a person in study

Patients can withdraw their consent and ask to withdraw from the study at any time and for whatever reason. If a Patient discontinues the study before its completion, the investigator must document the reasons as completely as possible.

In fact, the investigator can temporarily or permanently discontinue the study treatment for any reason which is in the best interest of the Patient.

If a Patient is lost to follow-up, the investigator will make every effort to resume contact with that person.

4.5.2Discontinuation of part or of the entire study

Unexpected events or new information pertaining to the study strategy, in light of which the study objectives or clinical programme probably would not be achieved, can lead the sponsor to terminate the study.

In case of early permanent discontinuation of the study, the information will be sent by the sponsor within 15 days to the relevant country health agency and to the ethics committee or earlier according to local regulations.

5 SCREENING AND INCLUSION OF PERSONS FROM THE STUDY

5.1 Inclusion criteria

- Age \geq 18 years old;
- Scheduled for any cardiac surgery (elective surgery) with cardio-pulmonary bypass, aortic clamp and cardioplegia, with median sternotomy and bi-pulmonary ventilation (cardiac valvular surgery (valve replacement or repair), coronary artery surgery, ascending aortic surgery and/or combined);
- Written informed consent.

5.2 Non-inclusion criteria

- Emergency surgery ;
- Planned thoracotomy with one lung ventilation;
- Patients with known respiratory diseases (current respiratory infections, asthma, chronic obstructive or restrictive pulmonary disease, obstructive apnea syndrome);
- Patients already intubated in the peri-operative period ;
- Immunodepression defined by proven humoral or cellular deficiency, by continuous administration of steroids at any dose for more than one month prior to hospitalization, high-dose steroids (> 15 mg / kg / day of methylprednisolone or Equivalent), radiotherapy or chemotherapy in the previous year ;
- Need for vasopressor or inotropic agents before surgery ;
- Any acute infection in the last month before surgery ;
- Hematological disorder, autoimmune disease, immunodeficiency, immunosuppressive therapy ;
- Heart failure with an left ventricular ejection fraction<35%;
- Protected person (adults legally protected (under judicial protection, guardianship, or supervision), person deprived of their liberty.

5.3 Methods of recruitment

Informed consent will be obtained the day of consultation for cardiac surgery or before randomization the day of surgery.

6 TREATMENTS ADMINISTERED IN THE STUDY

6.1 Authorised treatments

Besides immunosuppressive drugs listed below, every treatment are authorized during the study period.

6.2 Unauthorised treatments

Only immunosuppressive drugs within 7 days following cardiac surgery.

6.3 Emergency treatment

All emergency treatment required during anesthesia are allowed in the study.

7 EVALUATION OF SAFETY

7.1 Definitions

- Adverse event (AE): any untoward medical occurrence in a person who is a Patient in a research involving the human person study, whether or not this occurrence is related to the study.
- Serious Adverse Event (SAE): Severity is defined as one of the following occurrences :
 - . Death
 - . A life-threatening condition
 - . persistent or significant disability or incapacity
 - . Hospitalisation
 - . Prolongation of hospitalisation
 - . Malformation/congenital anomaly
 - . Potentially serious event (an adverse clinical event or a laboratory test result with a serious feature or considered as such by the investigator)
- Adverse Reaction (ADR): any untoward and unintended reaction linked to the study.
- Serious adverse reaction (SAR): a serious adverse event with a causal relationship to the study.
- Unexpected adverse reaction: an adverse reaction whose type, severity, intensity or outcome does not agree with informations contained in the protocol.

- Causal relationship: relation between the AE and the study. An Adverse Event related to the the study will become an AR.

7.2 Investigator's role

7.2.1Notification of serious adverse events

Every serious adverse event related to the study strategy or not, expected or unexpected, expect those mentioned on the paragraph 7.2.3, must be reported within 24 hours by the investigator to the sponsor on a "Serious adverse event" form on which will be indicated the date of occurrence, criterion of severity, intensity, relationship with the strategy evaluated (or the study), and the outcome.

It must be sent by fax to the number indicated on the form. The person in charge of Pharmacovigilance is [name] ([contact], e-mail: [contact]).

The period in which serious adverse events should be reported begins from the day of the written informed consent to the last visit of the patient.

The narrative must be completed and sent to the sponsor as soon as new relevant information is obtained. Copies of the patient's medical record must be attached as well as results of laboratory tests.

Whenever a serious adverse event persists at the end of the study, the investigator must follow the patient until the event is considered resolved.

7.2.2Notification of non-serious adverse events

All other Adverse Events, except those mentionned on the paragraph 7.1.3, will be reported on the "adverse event" page of the case report form specifying the date of occurrence, the description, severity, duration, method of resolution, causal relationship and the decisions made.

7.2.3Protocol specific features

The following events: postoperative infections will be recorded as primary evaluation criterion in the case report form and not as adverse events. Indeed, for this trial where efficacy endpoint can also be SUSARs, the integrity of the clinical trial may be compromised if the blind is systematically broken. Under these circumstances, the sponsor will treat postoperative infections as disease related and not subject to systematic unblinding and expedited reporting (Detailed guidance on the collection, verification and presentation of adverse event/reaction reports arising from clinical trials on medicinal products for human use ('CT-3') (2011/C 172/01) paragraph 7.11.1). As planned in the study, they will be analysed at the time of interim analyses (two interim analyses after inclusion of 1/3 and 2/3 of the patients) which will permit to show potential difference between the two groups during the study.

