1.9 Independent Data and Safety Monitoring Board

An independent Data and Safety Monitoring Board will be constituted at the beginning of the study with 5 members who are not involved in the study, including an intensivist, an anesthesiologist, a cardiac surgeon, an infectiologist, a methodologist/statistician.

In order to prematurely stop the study in case of efficacy, two interim analyses are planned. These analyses will be performed on the primary endpoint but will also evaluate safety data in order to rapidly detect any unexpected serious adverse events.

The Data and Safety Monitoring Board will meet after each interim analysis and at the end of the study. It can also meet on request of the coordinating investigator or the methodologist if serious adverse events or results which can jeopardize the existence of the protocol occur.

The Data and Safety Monitoring Board will propose to stop the study if the interim statistical analyses reach significance or if it appears that study continuation would be contrary to ethics rules (occurrence of serious adverse events, publication of trial results providing the answer to the question...).

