1.10 Independent validation committee

The validation committee will include 3 members, an infectiologist, a bacteriologist, and an intensivist. They will be in charge to validate the occurrence of nosocomial infections and the date of occurrence and will be blinded to the study arm (blinded evaluation of the primary endpoint). They will be provided with a standardized patient record containing all required document necessary harmonize patients' evaluations.

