4.3.2 Methods of blinding

This project is a randomized single-blinded (patient) trial.

4.4 Expected duration of participation of persons and description of chronology and of duration of all study periods including monitoring, if applicable

Recruitment period: 24 months

Duration of patient monitoring: 28 days

Duration of analysis of data: 6 months

Estimated total duration of study: 31 months

Starting with inclusion of the first patient, the sponsor has to inform without delay the local health agency and the ethics committee of the actual date of start-up of the study. The actual date of start-up = date of signature of consent form by the first person who is a Patient in the study.

The date of end of the study will be transmitted by the sponsor to the ethics committee and to the local health agency within 90 days or earlier according to local regulations. The date of end of the study corresponds to the last visit of the last person who is a Patient in the study.

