8.1 Description of planned statistical methods, including schedule of planned interim analysis

8.1.1Descriptive analysis

A first overall descriptive analysis and analysis by group will be performed. This consists of separate estimates, numbers and percentages for qualitative variables, means, standard error, medians and interquartile intervals for quantitative variables. The normal feature of the distribution of quantitative variables will be checked (Shapiro test).

8.1.2Comparison of groups at inclusion

Student's t test or a Mann-Whitney test if necessary will be used to compare quantitative variables, and a Chi² or Fisher's exact test if necessary will be used to compare qualitative variables between two groups at inclusion.

8.1.3Analysis of the primary criteria

The primary endpoint (rate of nosocomial infection at day-28 after CPB) will be compared between the two groups with the Chi²test.

Two interim analyses after inclusion of 1/3 and 2/3 of the patients, and one final analysis are planned. Stopping rules will use the alpha spending function with the O'Brien-Fleming boundary. The cumulative values of alpha for each analysis are: 0.00021 at the first analysis, 0.01202 at the second analysis and 0.04626 at the final analysis (nTerim, V1.1, Statistical solutions Ltd, Cork, Ireland). The trial will be stopped early if the significance of the Chi² test is below these alpha values.

8.1.4Analysis of other criteria

For the analysis of the other endpoints, the same strategy as for baseline comparisons will be used.

In addition, censored endpoints (survival) will be compared using the log-rank test.

Continuous endpoints repeatedly measured during the study will be compared using a repeated measure two-way (time, group) analysis of variance.

For all these analyses, adjustments can be made in case of heterogeneity at inclusion.

8.1.5Analysis of adverse events

Possible adverse events are coded according to the MedDRA classification and are the patient of a descriptive analysis.

8.2 Planned number of persons to be enrolled in the study, and planned number of persons in each centre with its statistical justification

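### Section 7.2.3 exempts all postoperative infections from AE/SAE reporting on a blinding argument that fits this trial poorly, leaves fatal infections unclear, and relies on interim looks with no harm guideline

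*Combined protocol and SAP*

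**What the plan says.** **The exemption.** Section 7.2.3 states that "postoperative infections will be recorded as primary evaluation criterion in the case report form and not as adverse events". Section 7.2.1 mirrors this: every SAE, "expect those mentioned on the paragraph 7.2.3, must be reported within 24 hours by the investigator to the sponsor" (the first word is evidently meant as *except*). Neither section makes an exception for fatal or life-threatening infections. Section 7.1 lists death and a life-threatening condition among the SAE criteria.

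**The reason given.** Efficacy endpoints might also qualify as SUSARs, and "the integrity of the clinical trial may be compromised if the blind is systematically broken".

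**Who is blinded.** Section 4.3.2: "This project is a randomized single-blinded (patient) trial". Section 1.10 adds that the validation committee adjudicating infections does not know the arm. Nothing describes the investigator or the sponsor as blinded.

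**The substitute.** Section 7.2.3 says infections will be analysed at the two interim analyses, "which will permit to show potential difference between the two groups during the study". Section 1.9 gives the purpose of these looks as early stopping for efficacy, with safety data also evaluated. The numerical rule is in 8.1.3: thresholds of 0.00021, 0.01202 and 0.04626, and "The trial will be stopped early if the significance of the Chi² test is below these alpha values". The rule names no direction and there is no separate harm guideline.

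**Unscheduled DSMB meetings.** Section 1.9 allows them "on request of the coordinating investigator or the methodologist if serious adverse events" occur; the same sentence goes on to include results that put the protocol itself at risk.

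**The concern.** Exempting endpoint events from expedited reporting can be legitimate, but the exemption needs a reason that fits the design, clear limits, and a substitute that does the job. All three are weak here.

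- The reason is to protect a blind, but the people who would send and receive the report are not described as blinded.
- The limits are unclear. A site that sees a death from mediastinitis or pneumonia can read 7.1 with 7.2.1 as requiring a 24-hour report, or 7.2.3 as exempting it. Sites may differ, and an unreported case would not count as an SAE under 1.9.
- The substitute is a pair of efficacy looks with very strict early thresholds.

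Infection is the outcome the intervention is meant to change, and the protocol does not treat harm as impossible: its rationale on pulmonary dysfunction (2.1, part B) accepts that mechanical ventilation can injure the lung and cause inflammation that leads to immunosuppression. If ventilation raised infections moderately, a large part of the trial could be enrolled before any stated rule reacted.

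**Working it through.** **1. Does the blinding reason fit?** Three groups matter.

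- Patients are blinded (4.3.2). A form sent from site to sponsor does not reach them.
- Adjudicators are blinded (1.10). They work from a standardized patient record, and an SAE form need not be part of it.
- Investigators and the sponsor are not described as blinded, so no documented blind is broken by the report.

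**2. Reproducing the plan's own figures.** Inputs from 8.1.3 and 8.2: 15% vs 10%, two-sided 5%, 80% power, looks at 1/3 and 2/3.

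- Fixed design: n = [1.960·√(2·0.125·0.875) + 0.842·√(0.15·0.85 + 0.10·0.90)]² / 0.05² = 686 per arm, 1372 in total.
- O'Brien-Fleming-type spending, 4[1 − Φ(z₀.₉₈₇₅/√t)] at t = 1/3, 2/3, 1, gives cumulative alpha 0.00021, 0.01210, 0.05. The per-look two-sided levels are 0.00021, 0.01202, 0.04626 (z ≈ 3.71, 2.51, 1.99). These are the plan's values, although 8.1.3 calls them cumulative.
- With these three looks, 80% power needs 695.5, so 696 per arm: the stated 1392.

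**3. Chance of crossing the stated threshold for harm.** Of the 1400 to be included, about 467 are in at look 1 and 933 at look 2. Assuming 1:1 allocation, that is about 233 and 467 per arm. The control rate of 15% is from 8.2. The ventilated rates are assumptions; the documents give no harm scenario.

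P(cross) = Φ{[Δ − z·√(2p̄(1−p̄)/n)] / √[(p₁(1−p₁) + p₂(1−p₂))/n]}

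For 15% vs 20%, the mirror image of the planned effect (p̄ = 0.175):

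- Look 1, n = 233: (0.05 − 3.707 × 0.03520) / 0.03513 = −2.29, so 1.1%.
- Look 2, n = 467: (0.05 − 2.512 × 0.02487) / 0.02481 = −0.50, so 30.8%.

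Simulation of 400,000 trials per scenario agrees with the formula to within about one percentage point for the rates shown. Rounded simulation results:

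| Assumed ventilated rate | Stated rule, look 1 | Stated rule, by look 2 | One-sided 0.025, look 1 | One-sided 0.025, look 2 |
|---|---|---|---|---|
| 17.5% | 0.1% | 7% | 11% | 18% |
| 20% | 1% | 31% | 30% (formula 29%) | 52% |
| 22.5% | 5% | 67% | 55% | 84% |
| 25% | 15% | 91% | 78% (formula 77%) | 97% |

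With control observed at 15%, crossing for harm needs about 29% on ventilation at look 1 (about 68 vs 35 infections) and about 21.4% at look 2 (about 100 vs 70).

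**4. What this means in patients.** A true 5-point excess means about 0.05 × 233 = 12 extra infections by look 1 and 0.05 × 467 = 23 by look 2. With even accrual over 24 months (an assumption), the looks fall near months 8 and 16, before the 28-day follow-up of the last patients counted.

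**5. False flags from a harm guideline.** With no true difference, one-sided 0.025 at each of two looks (correlation √(1/2) between the statistics) flags at least once with probability 4.2%.

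**The case against.** The strongest reply is that crossing a threshold is not the only way harm would be noticed, and this largely stands. The DSMB meets after each look with primary endpoint and safety data. It may propose stopping on ethical grounds, and may be convened for results that threaten the protocol, not only for SAEs. Section 7.3.5 requires immediate notification of any safety finding that alters the benefit/risk ratio, and 4.5.2 lets the sponsor terminate on unexpected events or new information. Section 7.2.3 promises only that a difference may become visible, not that a rule will stop the trial for harm. What remains is that none of these routes supplies infection counts by arm between looks, and none gives the DSMB a reference point for excess infection.

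Four stronger readings are tempting and are not supported:

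- *The trial has no blind to protect.* It does: patients and adjudicators are blinded. The point is that reporting need not touch either.
- *Fatal infections are definitely not reported.* The exemption covers them as worded, but death is an SAE criterion and 28-day mortality is recorded for all. The text is ambiguous rather than explicit.
- *A cluster of fatal infections would trigger nothing.* The routes above exist; what is missing is a clear, stated trigger.
- *Both looks are nearly useless for harm.* This is true of look 1 up to about a 7.5-point excess. Look 2 has a 91% chance of crossing for a 10-point excess.

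It is also fair that the suggested guideline is no cure: at look 1 it still misses about 70% of true 5-point excesses. By-arm reviews at further calendar intervals would be a matter of preference, and each added review raises the false-flag rate.

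**Conclusion.** The point holds as an inconsistency to resolve and a monitoring gap to fill; it does not show that the trial is unmonitored. The reason given in 7.2.3 does not match the blinding in 4.3.2 and 1.10. The handling of fatal and life-threatening infections is left open between 7.1/7.2.1 and 7.2.3. The only numerical rule at the looks would flag an assumed 5-point harm with about 1% probability at look 1 and 31% by look 2, after some 933 of 1400 patients. These figures rest on the 15% control rate, 1:1 allocation, looks at exactly 1/3 and 2/3 of 1400, and harm rates chosen for illustration. The change is worth making because it is cheap and concerns patient safety; the trial's efficacy inference is unaffected either way.

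**What to change.** **1. Reconcile 7.2.3 with 4.3.2, 7.1 and 7.2.1.** Remove the blinding argument, or restate it for the blind that exists. Keep non-fatal, non-life-threatening infections as endpoint events in the case report form. State that fatal and life-threatening infections are still notified to the sponsor as SAEs within 24 hours, so that they count as SAEs for convening the DSMB under 1.9.

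**2. Add a non-binding harm guideline to 8.1.3 and 1.9 at the two existing looks.** One example is one-sided p < 0.025 for excess infection with ventilation, prompting a DSMB discussion rather than an automatic stop. Under the same assumed rates of 20%, 22.5% and 25%, it flags about 29%, 55% and 77% at look 1, against 1%, 5% and 15% now. It spends no efficacy alpha.

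**Cost.** Wording in the protocol and any DSMB charter, a few more SAE forms, and about a 4% chance over the two looks of an unnecessary harm discussion when the arms do not differ. No change to sample size, efficacy thresholds or the number of looks.

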7.3 Sponsor's role

7.3.1Analysis of serious adverse events

The sponsor must evaluate the following:

- the causal relationship of serious adverse events (all adverse events for which the investigator or the sponsor considers that a causal relationship with the strategy can be reasonably considered, are considered as suspected adverse reactions. If the sponsor's evaluation of the event differs from the investigator's, both opinions are mentioned in the statement sent to the competent authority if this statement is necessary),
- and their expected or unexpected feature, using the reference document in force.

7.3.2Scoring of causal relationship

Conforming to the recommendations of ICH on the management of adverse events in clinical trials – ICH E2B (R3), version of May 12th, 2005 – an evaluation of the imputability is required for all declared SAE's.

7.3.3Declaration of unexpected serious adverse events

The sponsor reports all suspected unexpected serious adverse reactions (SUSAR) to ANSM (Agence Nationale de Sécurité du Médicament et des produits de santé), and to investigators within the regulatory time periods for reporting: if seriousness is death or life-threatening, SUSARs must be notified immediately; for other type of seriousness, SUSARs must be notified within 15 days (follow-up will be sent within 8 days).

7.3.4Transmission of annual safety reports

On the anniversary date of the first consent, the sponsor writes a safety report containing:

- the list of serious adverse events which may be related to the strategy studied, including expected and unexpected serious effects,
- a succinct and critical analysis of safety of patients who are Patients in the study.

It is sent to local regulatory agency and to the ethics committee within 60 days following the anniversary of the first consent.

7.3.5Declaration of other safety data

Every safety finding that can alter the benefit/risk ratio of the strategy or changes in conduct of the trial must immediately be notified to the sponsor. The report form will be the subject of an immediate report to the competent authorities (ANSM) and the ethic committee.

7.4 Expected adverse effects

No adverse effects are expected since several clinical studies, using the same ventilator strategies did not describe AE. No specific risks (individual or collective) are likely to occur:

- Maintaining MV during CPB did not hamper surgical procedure ;
- Several studies have found benefits to maintain MV, mainly in biological parameters; however no study has demonstrated its impact on postoperative infections.

Main constraints are blood withdrawn from patients. However, volume withdrawn will not induce any physical side effect.

8 STATISTICS

Statistical analysis will be performed on all randomized and evaluated patients (intention to treat analysis). It will be performed with SAS software (SAS Institute, Cary, NC, USA) in the Methodology/Biometrics department of the Inserm 1414 Clinical Investigation Centre of Rennes (certified ISO 9001 for the methodology, management and analysis of clinical studies).

